5.2 SECONDARY OBJECTIVES

Secondary objectives include:

- 1. Determining the safety of ondansetron in the study population.
- 2. Assessing the effective dose of ondansetron in other measures of success in the reduction of methamphetamine use including the proportion of successful subjects with 9 consecutive methamphetamine-free urine samples, the weekly mean proportion of non-use days assessed by self-report of use, the largest number of consecutive methamphetamine non-use days also assessed by self-report of use, and reductions in use as assessed by self-report compared to baseline (30 day history of use assessed by timeline followback).
- 3. Assessing the efficacy of ondansetron in reducing the severity of methamphetamine dependence [assessed by ASI-Lite (drug composite score principally, but composite scores of each section will also be analyzed, and the methamphetamine use question will be compared separately), and self and observer scored CGI, craving (assessed by BSCS), severity of depression as assessed by HAM-D, and withdrawal symptoms (assessed with a MAWQ)].
- 4. Assessing the efficacy of ondansetron in increasing the number of non-use days of other substances of abuse (marijuana, nicotine, and alcohol) as determined by self-report, and the number of negative urine specimens by individual drug (tetrahydrocannabinol, cocaine, amphetamines, barbiturates, opiates, and benzodiazepines), and the number of negative alcohol breathalyzer tests.
- 5. Assessing the effects of ondansetron on cognitive functions.
- 6. Collecting preliminary information on biological or psychosocial characteristics of patients who may show better responsiveness to ondansetron treatment. In particular, biological and psychological measures reflecting individual differences in serotonergic function.

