8.2 OUTCOME/RESPONSE MEASURES

Principal Outcome Measure: The principal outcome measure is quantitative urine methamphetamine analysis with a urine methamphetamine level ≥ 300 ng/mL being considered positive. This outcome measure was selected as the primary study endpoint to examine the effect of treatment on an objective measure of reduction in methamphetamine use. However, as methamphetamine has an excretion half-life of 12 to 14 hours, carryover could result in a positive urine specimen even when the subject has not used. Therefore, this is potentially a conservative outcome measure of treatment effect.

Data from previous methamphetamine pharmacokinetic studies as well as other outpatient studies will be used to develop rules/algorithm for determining new versus old (carryover) use utilizing urine methamphetamine levels. As the urine samples in this study are being analyzed quantitatively for methamphetamine, if an algorithm is developed to determine new use versus carryover, this algorithm will be used for additional analyses.

Secondary Outcome Measures Include:

- 1. Self-report of methamphetamine use (using the SUR);
- 2. Severity of methamphetamine dependence using the ASI-Lite (drug composite score principally, but composite scores of each section will also be analyzed, and the methamphetamine use question will be compared separately) and self and observer scored CGI;
- 3. Effect on craving (BSCS score);
- 4. Effect on depression (Ham-D score);
- 5. Effect on withdrawal symptoms (MAWQ score);
- 6. Use days of other substances of abuse (marijuana, nicotine, and alcohol) as determined by self-report (SUR), negative urine results (tetrahydrocannabinol, cocaine, amphetamines, barbiturates, opiates, and benzodiazepines), and breathalyzer results (alcohol);
- 7. Cognitive function tests; and
- 8. Safety of ondansetron in the study population (adverse events, ECG, and clinical laboratory studies.

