Depending upon the assessment schedule, urine samples will be collected and aliquoted into the appropriate number of specimens. One specimen will be held frozen at the clinical site as a backup. The others will be tested immediately or will be frozen as appropriate. Specimens will be collected and tested as follows:

Methamphetamine, Creatinine, Tetrahydrocannabinol, Cocaine, Amphetamines, Barbiturates, Opiates, and Benzodiazepines Analysis.

During the screening and baseline period of the study, urine will be collected 3 times per week (generally Monday, Wednesday, and Friday, barring holidays and schedule conflicts). Upon randomization, the urine samples collected from subjects during the screening/baseline period will then be sent to NWT. NWT will screen the 1st sample of the week for cocaine, tetrahydrocannabinol, methamphetamine/amphetamines, barbiturates, opiates, benzodiazepines and creatinine. NWT will screen the 2nd and 3rd samples of the week for amphetamines/methamphetamine and creatinine only, and NWT will do quantitative analysis for

Version No.: 3, Date: 22 May 2002

methamphetamine and amphetamines for all the samples screened positive by NWT for methamphetamine/amphetamines.

Note: The sites will store samples from screening until the subject is randomized, and once randomized then samples can be sent to NWT for analysis.

Following randomization, during the treatment phase of the study and at each of the follow-up visits, urine will be collected 3 times per week (generally Monday, Wednesday, and Friday, barring holidays and schedule conflicts) and NWT will screen the first sample collected each week for cocaine, methamphetamine/amphetamines, tetrahydrocannabinol, barbiturates, opiates, and benzodiazepines. NWT will screen all samples for amphetamines/methamphetamine and quantitative creatinine, and NWT will quantitate amphetamines and methamphetamine for all samples which screen positive by NWT for methamphetamine/amphetamines.

All specimens collected during this time frame and screened positive by NWT for methamphetamine/amphetamines will be subjected to methamphetamine quantitative analysis performed at NWT for the determination of "new use." The back-up sample retained at the site will be stored frozen until the NIDA data-coordinating center has notified the site that it can be disposed.

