Urine Toxicology Screen Using an Onsite Testing Device. During the screening and baseline period, urine will be collected 3 times per week (generally Monday, Wednesday, and Friday, barring holidays and schedule conflicts). After the backup aliquot and central laboratory testing aliquot has been taken, these samples will be analyzed using an on-site testing device (tetrahydrocannabinol, methamphetamine, cocaine, amphetamines, barbiturates, opiates, benzodiazepines, phencyclidine, and tricyclics). Samples positive for amphetamine (the onsite testing device has a cutoff of ≥ 1000 ng/mL) will be considered as positive for methamphetamine for inclusion criteria purposes.

During treatment and after the backup aliquot and central laboratory testing aliquot has been taken, the first urine sample collected each week will be analyzed using an on-site testing device (tetrahydrocannabinol, methamphetamine, cocaine, amphetamines, barbiturates, opiates, benzodiazepines, phencyclidine, and tricyclics).

A frozen aliquot of every sample will be stored at the site. At treatment termination and followup, samples will be sent to a central lab for analysis, be subjected to onsite testing, and an aliquot will be frozen on site as back up. Results of on-site testing will be provided to the clinical staff as well as the investigative staff for the safety of the subjects.

Medical Urinalysis. Urine will be collected and analyzed for specific gravity, pH, blood, protein, glucose, ketones, leukocytes, and nitrites. The analysis will be conducted at a central clinical laboratory.

Urine Pregnancy Test. An onsite qualitative urine pregnancy test that evaluates human β -chorionic gonodotropin will be used.

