15.1.2 Secondary Outcomes Measures

Effect on methamphetamine and other drug use during the 8 week treatment period

- B. Proportion of subjects with 3 consecutive weeks of abstinence as measured by 9 consecutive methamphetamine-free (<300 ng/ml) urine samples.
- C. Weekly mean proportion of methamphetamine non-use days based on subject's self report of use (SUR) during the 8-week treatment period.

- D. The proportion of subjects who decrease the overall proportion of methamphetamine use to 50% or less of their use in the month prior to the study based on timeline followback for the before study period and self report using the SUR during the on study period.
- E. The maximum number of consecutive methamphetamine non-use days by subject's self report of use (by SUR).
- F. The number of methamphetamine-free urines during the 8-week period.
- G. Weekly mean proportion of non-use days of other drug use, by other drug according to SUR including marijuana, nicotine, and alcohol.
- H. Number of negative urines for tetrahydrocannabinol, cocaine, amphetamines, barbiturates, opiates, and benzodiazepines, and negative alcohol breathalyzer tests.
- H. Log weekly median quantitative urine methamphetamine levels.
- I. Proportion of subjects who reduce overall median of methamphetamine quantitative urine concentration to 50% of his/her baseline values.
- J. Proportion of subjects who reduce the overall median of methamphetamine quantitative urine concentration to 25% of his/her baseline value.

Reduction in the severity of methamphetamine dependence, craving, and withdrawal

- K. CGI-O scores (dependence).
- L. CGI-S scores (dependence).
- M. ASI-Lite composite score of the drug section and methamphetamine use question individually (dependence) and composite scores of the other sections (other global measures of improvement).
- N. BSCS scores (craving)
- O. MAWQ scores (withdrawal)

Severity of Depression

P. HAM-D scores.

Changes in Cognitive Functions

Q. Change in cognitive function at study end compared to baseline.

Treatment Retention

R. Number of days in treatment.

Safety of Ondansetron

S. AEs, laboratory data, physical exams, ECG results, and vital signs.

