15.2.2 Secondary Efficacy Outcomes

It is hypothesized that ondansetron as compared to placebo will increase the proportion of successful subjects, the weekly mean proportion of methamphetamine non-use days according to self-report alone, the number of methamphetamine negative urine samples, and the weekly mean proportion of other drug non-use days or alcohol according to self-report and proportion of negative urines for other drugs use or negative breathalyzer tests. It is further hypothesized that ondansetron will reduce the severity of methamphetamine dependence, craving, and withdrawal and depression as assessed by ASI-Lite, BSCS, CGI-S, CGI-O, MAWQ, and HAM-D.

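### Amphetamine-negative urines are counted as an other-drug outcome, so the amphetamine line can carry a methamphetamine effect and be misread as an effect on other drugs

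*Protocol*

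**What the plan says.** Protocol 5.2, secondary objective 4, begins "Assessing the efficacy of ondansetron in increasing the number of non-use days of other substances of abuse". Its urine component is "the number of negative urine specimens by individual drug (tetrahydrocannabinol, cocaine, amphetamines, barbiturates, opiates, and benzodiazepines", followed by breathalyzer tests for alcohol. Section 8.2, outcome measure 6, groups the results in the same way: "Use days of other substances of abuse (marijuana, nicotine, and alcohol) as determined by self-report (SUR), negative urine results (tetrahydrocannabinol, cocaine, amphetamines", and so on. The first outcome H in 15.1.2 repeats the list as "Number of negative urines for tetrahydrocannabinol, cocaine, amphetamines, barbiturates, opiates, and benzodiazepines". Section 15.2.2 then hypothesizes that ondansetron raises the "proportion of negative urines for other drugs use or negative breathalyzer tests", and names this separately from the number of methamphetamine-negative samples.

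Elsewhere the two analytes are tied together. Inclusion criterion 4 (9.1) is met by a urine positive for either one. Section 13.6.20 says that an onsite amphetamine positive "will be considered as positive for methamphetamine for inclusion criteria purposes". For the treatment phase the same section states that "NWT will screen all samples for amphetamines/methamphetamine and quantitative creatinine"; amphetamines and methamphetamine are then quantitated in the samples that screen positive.

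**The concern.** Every participant is methamphetamine dependent. At entry, an amphetamine signal is taken as evidence of methamphetamine use; at outcome, the same signal is counted as use of a different drug. No section says which assay feeds the amphetamine count in H, and none sets aside amphetamine positives that accompany methamphetamine.

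The other-drug hypothesis in 15.2.2 is a claim beyond the primary one: that ondansetron also reduces use of other substances. If ondansetron lowered methamphetamine use and did nothing else, the amphetamine line could still favour ondansetron and be cited in support of that further claim. Methamphetamine-free urines are already the primary outcome (15.1.1) and the count in outcome F (15.1.2), so the same effect could be reported again under a label that does not fit it.

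**Working it through.** The protocol gives no figure to reproduce here. The point rests on comparing sections, with a short calculation to show how the error scales.

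**Step 1: how amphetamine is classified.**

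| Section | Treatment of amphetamine |
|---|---|
| 5.2 objective 4; 8.2 measure 6 | one of the other drugs of abuse |
| 15.1.2, first H | one of six drug classes counted; methamphetamine is not among them |
| 15.2.2 | negative urines for other drugs are an efficacy hypothesis |
| 9.1 criterion 4 | qualifies in place of methamphetamine |
| 13.6.20, onsite device | an amphetamine positive is read as methamphetamine, for eligibility |
| 13.6.20, central laboratory | one combined screen, then both analytes quantitated if positive |

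The first three rows treat amphetamine as a drug distinct from methamphetamine. The last three do not keep the two apart at entry or at the screening stage.

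**Step 2: how a methamphetamine effect passes through.** Let p_P and p_A be the proportions of methamphetamine-positive samples on placebo and on ondansetron. Let c be the share of these that also read amphetamine-positive. Assume that c is the same in both arms and that there are no amphetamine positives from any other source. Then:

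- amphetamine-negative proportion = 1 − c·p
- spurious difference (ondansetron minus placebo) = c·(p_P − p_A)

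**Step 3: illustration.** The protocol gives neither rate (15.5 says there are no data on the effect), so assume p_P = 0.60 and p_A = 0.40, with no true effect on any other drug. Assume also that one sample per week is scored, giving 8 in total.

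| c | Spurious difference, percentage points (20·c) | Expected amphetamine-negative urines of 8, placebo: 8(1 − 0.6c) | Ondansetron: 8(1 − 0.4c) | Difference |
|---|---|---|---|---|
| 0 | 0 | 8.0 | 8.0 | 0 |
| 0.25 | 5 | 6.8 | 7.2 | 0.4 |
| 0.5 | 10 | 5.6 | 6.4 | 0.8 |
| 0.75 | 15 | 4.4 | 5.6 | 1.2 |
| 1 | 20 | 3.2 | 4.8 | 1.6 |

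**Step 4: what can be said about c.** The document gives no value. If H is scored from the quantitated amphetamine level or from the onsite panel, c could lie anywhere in the range. If H is scored from the combined screen, c is close to 1: methamphetamine is quantitated only after that screen is positive, so a sample recorded as methamphetamine-positive has already failed to be negative on the combined screen.

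**The case against.** Several arguments on the other side are sound and limit the point.

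- **The eligibility rule is narrow.** The statement in 13.6.20 that equates amphetamine with methamphetamine covers inclusion only. A reader might infer that the protocol equates the analytes throughout, but it does not: the onsite panel lists them separately and the central laboratory quantitates both. For the treatment phase, the support is the combined screen alone.
- **Reporting is by drug.** Objective 4 calls for counts by individual drug, and no section pools them. The tetrahydrocannabinol, cocaine, barbiturate, opiate and benzodiazepine lines are untouched. This does not protect the amphetamine line, which is the one open to misreading.
- **The overlap is unknown.** A reader might infer that the amphetamine count is largely the primary outcome under another name. No section says how often a methamphetamine-positive urine also reads amphetamine-positive, so that cannot be claimed.
- **Sampling for H is not stated.** A reader might infer that amphetamine is counted on all three weekly samples and the other drugs on one. Section 13.6.20 says which samples are screened, not which feed H. The drugs in H are those on the once-weekly central panel, so a weekly count is an equally natural reading.
- **The outcome is secondary, in a pilot.** Dose selection under 15.4.3 uses the primary outcome and adverse events.

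The choice of assay and cutoff for H could properly be left to a statistical analysis plan. The drug list and the hypothesis it serves are fixed in the protocol itself, and that is where the misclassification lies.

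**Conclusion.** The point holds for one line of one secondary outcome. With amphetamines on the other-drug lists, a pure methamphetamine effect can appear in the amphetamine line of the first outcome H and be taken as support for the other-drug hypothesis in 15.2.2. Its size is c times the methamphetamine difference, with c from 0 to 1. The 60% and 40% rates behind the 0 to 20 point range are assumptions for illustration, not protocol figures. Any c above 0 carries some of the effect across. The primary analysis is not affected, and neither are the other drug lines when reported individually. The change is still worth making, because it bears on what the trial may conclude about other drugs and costs almost nothing.

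**What to change.** Delete amphetamines from the other-drug lists in 5.2 (objective 4), 8.2 (measure 6) and 15.1.2 (the first H; the letter is used twice, so the amendment should say which is meant). Report amphetamine results beside the methamphetamine outcomes as supportive data. Section 15.2.2 names no individual drugs for its urine hypothesis and needs no change on this point.

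The cost is a wording change in three places, with no new sample, visit or assay. The small downside is that genuine use of amphetamine alone would no longer count as other-drug use, though it would still be visible in the supportive results.

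Keeping amphetamine in H but counting it only when the same sample is methamphetamine-negative is not recommended. That rule conditions on a status that treatment may change: if ondansetron lowered methamphetamine use, more of its samples would become able to count, and unchanged amphetamine use could look like an increase.

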15.2 STATISTICAL HYPOTHESES

15.2.1 Primary Efficacy Outcome

It is hypothesized that ondansetron as compared to placebo will decrease the weekly proportion of methamphetamine positive urine specimens over the treatment period.

15.2.2 Secondary Efficacy Outcomes

It is hypothesized that ondansetron as compared to placebo will increase the proportion of successful subjects, the weekly mean proportion of methamphetamine non-use days according to self-report alone, the number of methamphetamine negative urine samples, and the weekly mean proportion of other drug non-use days or alcohol according to self-report and proportion of negative urines for other drugs use or negative breathalyzer tests. It is further hypothesized that ondansetron will reduce the severity of methamphetamine dependence, craving, and withdrawal and depression as assessed by ASI-Lite, BSCS, CGI-S, CGI-O, MAWQ, and HAM-D.

15.2.3 Other Hypotheses

We hypothesize that measurement of platelet serotonin transporter genotype in tandem with psychosocial assessment of baseline characteristics related to serotoninergic functioning of subjects (i.e. impulsivity) will identify subgroups that may differentially respond to ondansetron. Separate subset analysis of these populations may be of interest depending upon the results of the primary analysis.

It has been hypothesized that ondansetron responsiveness may be associated with polymorphic variation in the serotonin transporter (Johnson *et al.*, 2000). According to the hypothesis, individuals with the homozygous LL-type (or long form) of the transporter may respond to ondansetron whereas patients with the dominant short form allele (SS or SL allelic forms) may not. Also, it is possible that other genetic polymorphisms in co-related neurotransmitter systems (e.g. opioid) also may interact with the serotonin system. Since this pharmacogenomic approach to treatment is developing rapidly, and all possibilities are not currently evident, we propose to collect and archive DNA for future analysis investigating the relationship between ondansetron and genetic polymorphisms at multiple neurotransmitter targets.

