5 STUDY OBJECTIVES

5.1 PRIMARY OBJECTIVES

The primary objective of this study is to conduct a preliminary assessment of the possible efficacy of ondansetron to reduce methamphetamine use in outpatients with methamphetamine dependence. The hypothesis is that ondansetron treatment compared to placebo will decrease the weekly proportion of methamphetamine positive urines. The results of this study will be used to design subsequent larger studies to confirm the efficacy of ondansetron. This study is also intended to gather preliminary information on biological or psychosocial characteristics of patients who may show better ondansetron treatment responsiveness.

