15.7 POST HOC ANALYSES

Data will be collected in this study for scientific use and not as primary or secondary outcome measures. This includes SERT genotype, HRBS, BIS, and SSS assessments. Additional *post hoc* analysis may be performed to evaluate other confounding factors on outcomes such as age or patterns of methamphetamine use at baseline and after treatment.

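### The genotype and impulsivity responder question is a stated objective, but section 15.2.3 leaves its analysis optional after the primary result is seen and names separate subsets, which do not estimate a difference in response.

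*Protocol*

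**What the plan says.** Section 5.1, under the primary objectives, states: "This study is also intended to gather preliminary information on biological or psychosocial characteristics of patients who may show better ondansetron treatment responsiveness". Section 5.2 item 6 repeats this as a secondary objective ("Collecting preliminary information on biological or psychosocial characteristics of patients who may show better responsiveness to ondansetron treatment") and adds: "In particular, biological and psychological measures reflecting individual differences in serotonergic function".

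Section 15.2.3 hypothesises that SERT genotype in tandem with impulsivity will pick out subgroups that respond differently. It reports the genotype part as an existing hypothesis: "individuals with the homozygous LL-type (or long form) of the transporter may respond to ondansetron". S-carriers (SS or SL) are the suggested non-responders. The analysis is covered by one sentence: "Separate subset analysis of these populations may be of interest depending upon the results of the primary analysis".

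Section 15.4.2 puts dose level, prior use, age of onset, gender, ADD diagnosis and alcohol use into the model with their treatment interactions, with no condition on the primary result. Genotype, BIS and the Sensation Seeking Scale (SSS) are not in that list. Section 15.7, which names SERT genotype, HRBS, BIS and SSS, says: "Data will be collected in this study for scientific use and not as primary or secondary outcome measures". Section 8.2 likewise gives them descriptive and other scientific use. Genotyping is optional and consented separately (section 13.6.31).

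**The concern.** The measures that item 6 singles out get the weakest analysis in the plan. There are two separate faults.

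- **The condition.** Whether the analysis is run depends on the primary result, and no rule says how. The choice would be made with the primary result in hand. An effect confined to one genotype is diluted in the overall comparison, so the overall result is a poor guide to whether the responder question deserves an answer.
- **The method.** Differential response is a contrast between subgroup effects, that is, an interaction. Estimating each subset separately gives two effects and no estimate or interval for their difference.

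Section 5.1 says the results will be used to design larger studies, so an unreported or selectively reported responder signal would carry forward. Section 16.3 says the analysis follows the analytical plan section of the protocol, so the wording of section 15 matters even if a separate analysis plan exists.

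**Working it through.** **Inputs from the protocol.** Two-sided 5% tests (15.4.1); four arms, 30 evaluable and 45 randomised per arm, 30% not evaluable (15.5). No effect size or power is stated.

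**The plan's own figure.** 30/(1 − 0.30) = 42.9, so 43 per arm. The stated 45 is rounded up: 45 × 0.70 = 31.5 evaluable. Thirty per arm is a fair basis.

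**Assumptions, not in the documents.** LL share q = 0.20 to 0.40; effect d = 0.8 SD in LL and zero in S-carriers; SD = 1; all subjects genotyped; normal approximation on a continuous scale rather than the ordinal GEE; 30 placebo against 90 pooled active.

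**Overall comparison.** Effect = q × d. SE = √(1/30 + 1/90) = 0.211. Power = Φ(qd/SE − 1.96) + Φ(−qd/SE − 1.96).

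**Genotype-by-treatment test.** SE = √[(1/q + 1/(1−q)) × (1/30 + 1/90)], contrast = d.

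| LL share | Overall effect (SD) | Power, pooled | Non-significant | Interaction SE (SD) | Interaction power |
|---|---|---|---|---|---|
| 0.20 | 0.16 | 11.8% | 88% | 0.53 | 33% |
| 0.30 | 0.24 | 20.7% | 79% | 0.46 | 41% |
| 0.40 | 0.32 | 32.9% | 67% | 0.43 | 46% |

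For one dose against placebo at 30 per arm, power is 9.5%, 15.3% and 23.6% in the same order.

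**Wider range.** With q from 0.2 to 0.5 and d of 0.5, 0.8 or 1.0 SD, the pooled overall comparison is non-significant in about 34% to 92% of trials. Interaction power is 16-22%, 33-48% and 48-66% respectively.

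**Comparing the two tests.** The ratio of the interaction z to the overall z is √[(1−q)/q], which is at least 1 for q up to 0.5. If only a fraction g of subjects is genotyped, the interaction z shrinks by √g, and the advantage disappears once g falls below q/(1−q): 0.2/0.8 = 25% at q = 0.2, and 0.4/0.6 = 67% at q = 0.4.

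**Separate subsets.** Give both genotypes the same true effect of 0.5 SD (30 against 90).

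- q = 0.3: subset powers are 0.255 and 0.510. Exactly one is significant with probability 0.255 × 0.490 + 0.510 × 0.745 = 0.505.
- q = 0.5: both powers are 0.389. Exactly one is significant with probability 2 × 0.389 × 0.611 = 0.475.

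An interaction test would signal a difference in 5% of such trials.

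**The case against.** The case on the other side is substantial, and much of it stands.

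- A reader might infer that a null primary result cancels the responder analysis. The text does not say so. It is permissive and gives no direction, and a null result could equally prompt a search for responders. The 67-88% figure shows how uninformative the condition is under the hypothesis. It is not the probability that the analysis is dropped.
- A reader might infer that differential response would be claimed by comparing significance across subsets. No such rule is stated. The 48-51% discordance shows what could go wrong with that reading of subset results, not what the protocol commits to.
- A reader might take the cited alcohol trial (section 4.5) as evidence that a genotype-confined effect is expected. The subtype there is age of onset, which is already a randomisation stratum and an unconditional interaction term.
- Item 6 promises preliminary information, not a test, and section 15.4.2 serves it in part through the other characteristics. The blood sample also has a second stated purpose, archiving DNA for later work. Calling baseline measures something other than outcomes, as sections 8.2 and 15.7 do, is correct in itself.
- The genotype hypothesis is reported second-hand and hedged, and the trial's own hypothesis is joint with impulsivity.
- The better test would itself miss an 0.8 SD effect in more than half of trials.

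These points limit the concern without removing it. An analysis that serves a stated objective is still optional after the primary result, and the method named does not estimate the quantity hypothesised. How to model an exploratory subgroup could be left to an analysis plan, but here the protocol itself has fixed the condition and the form.

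**Conclusion.** The point holds as a worthwhile, inexpensive improvement to an exploratory part of the plan. The primary analysis and the listed secondary outcomes are unaffected. The documents support this much: the genotype and impulsivity analysis can be skipped, or chosen once the primary result is known, and separate subsets do not answer whether response differs.

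The figures for size rest on the assumed LL share and effect, on complete genotyping and on a continuous-scale approximation, so they are illustrative. The wording fault does not depend on them.

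**What to change.** In section 15.2.3, replace the conditional sentence with two exploratory terms added to the section 15.4.2 GEE model for the primary outcome:

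- genotype (LL against S-carrier) by treatment (pooled ondansetron against placebo);
- BIS total score by treatment.

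Run both whatever the primary result, in all subjects with the data, and report estimates with 95% confidence intervals labelled hypothesis-generating. State that any subset results are descriptive and not grounds for claiming differential response. Because the hypothesis is joint, a descriptive genotype-by-impulsivity summary may be added. Align section 15.7 so that the genotype and BIS analyses are no longer treated as purely post hoc.

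The cost is a wording change and two model terms on data already being collected, with no extra subjects, samples or visits. The downside is imprecision: for genotype the 95% interval half-width is about 1.96 × 0.43 = 0.84 to 1.96 × 0.53 = 1.03 SD under the assumptions above, and wider after refusals of optional genotyping.
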